## 4.10 Safety Evaluation

All safety summaries and analyses will be based on the Safety Set.

### 4.10.1 Extent of Exposure

A by-patient listing of exposure data will be provided.

### 4.10.2 Adverse Events

Adverse events will be coded using the MedDRA Version 23.0 or higher.

Treatment-emergent AEs (TEAE) are defined as AEs that either start or worsen in severity on or after the date/time of study drug administration and through the end of study. Partial date imputation was specified in [Section 4.3](#). Imputed dates will only be used for TEAE definition.

An overall summary table of TEAEs will be provided with the number and percentage of patients (incidence) reporting an event along with the total number of events presented for the following categories:

- All TEAEs,
- TEAEs related to Study Drug,
- TEAEs by severity,
- Severity grade 3 and higher TEAEs,
- Severity grade 3 and higher TEAEs related to Study Drug,

- Serious TEAEs,
- Study drug-related serious AEs (SAEs),
- Fatal TEAEs,
- TEAEs leading to study discontinuation,
- SAEs related to COVID-19,
- TEAEs suspected as infusion-related reactions.

#### 4.10.2.1 Adverse Event Summaries by System Organ Class and Preferred Term

The incidence and total number of events for the following will be summarized by SOC and PT, unless otherwise specify:

- All TEAEs,
- TEAEs related to Study Drug,
- TEAEs by maximum severity,
- TEAEs by maximum causality,
- TEAEs related to Study Drug by maximum severity,
- Severity grade 3 or higher TEAEs,
- Study drug related grade 3 or higher TEAEs,
- Serious TEAEs,
- SAEs related to Study Drug,
- Fatal TEAEs,
- TEAEs leading to study discontinuation,
- TEAEs suspected as infusion-related reactions,
- SAEs related to COVID-19.

Adverse event summaries will be ordered by decreasing incidence for SOC, and PT within SOC, in the ATYR1923 Total treatment group. In case of equal number of subjects sorting will be done alphabetically. Additionally all TEAEs will be summarized by PT only and will be ordered by decreasing incidence for PT in the ATYR1923 Total treatment group.

For each patient and each adverse event, the worst severity recorded will be attributed and used in the by-maximum-severity summaries. Similarly, the worst causality (most related to treatment) will be attributed and used in the by-maximum-causality summaries. If missing severity or causality will be imputed as stated in [Section 4.3.1](#).

#### 4.10.2.2 Adverse Event Listings

By-patient listings of all AEs will be provided. The following listings will be provided:

- All AEs,
- All drug-related AEs,
- All grade 3-5 AEs,
- All SAEs,
- All fatal AEs,
- All AEs leading to study discontinuation.

#### 4.10.3 Clinical Laboratory Evaluation

Local laboratories will be used for laboratory safety evaluations in this study. [Table 6](#) shows the list of laboratory parameters. Laboratory results will be graded as low, normal, or high comparing to the normal range provided by the local laboratories .

All laboratory values will be reported in local units and in alphabetical order.

For by-visit summaries, the first non-missing assessment (including repeat assessments) recorded at each visit will be used. Optional laboratory parameters (Creatine Phosphokinase, Lactate Dehydrogenase (LDH)) will not be summarized by treatment group, only listed. Separate summaries for Hematology, Clinical Chemistry, Coagulation, Urinalysis and Serology (Baseline only) to be produced will be:

- for laboratory values reported as a character value, such as 'negative', number and percentage of subjects for each outcome by scheduled visit
- for continuous laboratory values, number and percentage of subjects with values outside normal range by scheduled visit,
- for continuous laboratory values, shifts from baseline in relation to normal range at all scheduled visits.

By-patient listings of all laboratory data, with abnormal values flagged, will be provided for Serology, Hematology, Clinical Chemistry, Coagulation and Urinalysis test results. Further marker of anaphylaxis: Tryptase will be listed by subject.

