4.1.1. Assessments During Intubation

In the event that a patient requires intubation, SOC assessments and interventions will supersede study assessments for the duration of intubation, with the exception of the WHO Scale and sample collection for ADA and Jo-1 Ab, which will continue to be collected as per the Schedule of Assessments ([Table 1](#)) on Days 5, 7, 10, 14 and weekly thereafter. The following clinical assessments will be collected and analyzed as available per the institution's electronic medical records.

- Date and time of intubation and extubation.
- Adverse events (AEs) (including new infections). In the case of new infections, the site and source of culture are to be recorded.
- Concomitant medications.

Patients requiring intubation will have the assessments scheduled for Day 14 and/or Discharge performed at the time of hospital discharge and will attend Day 28 and 60 TC follow-up visits.

2 With the exception of the WHO Scale and sample collection for ADA and Jo-1 Ab, which will continue to be collected as per the Schedule of Assessments.

If the patient is hospitalized for ≥ 21 days, the Day 14 and/or Discharge assessments are to be performed weekly (Days 21, 28, 35, etc.) until discharge (with the exception of PK, which is to be done only at Day 28).

After discharge, the patient will proceed to the next scheduled outpatient TC follow-up visit. (Thus, if a patient remains hospitalized on Day 28, the Day 28 TC follow-up visit need not be conducted.)

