8.6.5. Safety Laboratory Tests

Blood and urine samples for clinical safety laboratory assessments will be collected at the time points designated in [Table 1](#) at Screening and Day 1. After Day 1, clinical safety laboratory assessments are to be collected per SOC. Note that if screening safety laboratory assessments are performed within 2 days of Day 1, then the pre-dose Day 1 safety laboratory assessments need not be repeated.

These samples will be analyzed at the local laboratory following their laboratory standard operating procedures (SOPs).

The following parameters may be collected and documented in the eCRF, as available per SOC:

- Clinical chemistry (serum quantitatively):
 - Total bilirubin, alkaline phosphatase, aspartate aminotransferase (AST), alanine aminotransferase (ALT), lactate dehydrogenase (LDH), creatine phosphokinase, albumin, creatinine, blood urea nitrogen, total protein, glucose, , sodium, potassium, calcium and chloride,.
- Hematology (blood quantitatively):
 - Leukocytes, erythrocytes, hemoglobin, hematocrit, thrombocytes, partial automated differentiation (lymphocytes, monocytes, eosinophils, basophils, neutrophils), mean corpuscular volume, mean corpuscular hemoglobin, mean corpuscular hemoglobin concentration
- Coagulation (blood quantitatively):
 - Prothrombin time (reported in seconds and as international normalized ratio) and partial thromboplastin time
- Urinalysis (semi-quantitative by dipstick):
 - Hemoglobin, urobilinogen, ketones, glucose, protein
 - Microscopy is to be performed if indicated by an abnormal and clinically significant result. Culture results, if conducted per SOC, are to be documented.

- Cardiac troponins, ferritin, B-type natriuretic peptide (BNP) or N-terminal-pro-BNP, and D-dimer.

In case of unexplained or unexpected clinical laboratory test values, the tests will be repeated as soon as possible and followed up until the results have returned to the normal range, baseline level and/or an adequate explanation for the abnormality is found. The clinical laboratory will clearly mark all laboratory test values that are outside the normal range and the Investigator will indicate which of these deviations are clinically significant. These clinically significant deviating laboratory results will then be recorded as AEs and the relationship to the treatment will be indicated (see also [Section 9.2](#)).

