10.1.2.3.2. Clinical Laboratory

Clinical laboratory data will be listed, and will also be flagged if the parameter is outside the reference range. A summary of all data outside the reference range of the clinical laboratory will be provided. Clinical laboratory data will be presented descriptively, where applicable.

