### 4.2 General Presentation Considerations

**Baseline:** the last available pre-treatment assessment, unless otherwise specify. All assessments should have time collected. If time is not collected and date of assessment is the same as study drug administration date then assessment will be assumed to be collected prior to treatment unless schedule of assessments and protocol indicate planned collection is always after dosing.

For baseline of oxygen use, total oxygen use in 24 hours before drug administration date.

**Day-of-Discharge (DoD):** day when patient is discharged from the hospital.

**Date of discharge:** date patient is discharged from the hospital.

**Early Termination (ET):** day when patient withdraws from the study before completion.

**End-of-Study (EOS):** the EOS assessment is at Day 60 for patients who complete the study.

**End of study date:** date of EOS assessment (Day 60) if patient completes the study or date of early withdrawal if patient discontinues early, or date of death.

**Study Day:** <Assessment Date> - study drug administration date + 1 if <Assessment Date> is on or after study drug administration date. <Assessment Date> - study drug administration date, if <Assessment Date> is before study drug administration date.

Durations are generally calculated as the stop date - start date +1, if not otherwise stated.

For elapsed time (eg, time since the initial diagnosis) is calculated as reference date - event date.

If more than one laboratory value is available for a given study day, the last valid observation will be used in summaries, unless otherwise stated. If it is not possible to determine which is the last measurement due to missing times, then the average of all measurements for that study day will be used as the value for that study day. All observations will be presented in listings.

Laboratory data will be presented in standard units.

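### The SAP 4.10.3 tables for continuous chemistry, hematology and coagulation values cannot show how far a value worsened, and laboratory collection during intubation is unclear

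*SAP*

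**What the plan says.** SAP 4.10.3 (Clinical Laboratory Evaluation) sets the three-level grading: "Laboratory results will be graded as low, normal, or high comparing to the normal range provided by the local laboratories". It also sets the value to use: "For by-visit summaries, the first non-missing assessment (including repeat assessments) recorded at each visit will be used". The first table for continuous results is "for continuous laboratory values, number and percentage of subjects with values outside normal range by scheduled visit". The second is a shift from baseline between the same range categories, again at scheduled visits. LDH and creatine phosphokinase are listed only. All laboratory data are listed by patient with abnormal values flagged.

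SAP 4.2 groups by-visit summaries by nominal visit: Days 1 to 7, 10, 14, 28 and 60. For several laboratory values on one day it says "the last valid observation will be used in summaries, unless otherwise stated". Below its Table 3 it also takes the latest non-missing result for a scheduled visit, with no exception stated. Section 4.2 calls for standard units, whereas 4.10.3 calls for local units.

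Protocol 10.1.2.3.2 commits the sponsor as follows: "A summary of all data outside the reference range of the clinical laboratory will be provided". It adds that laboratory data will be presented descriptively where applicable.

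On collection, Protocol 8.6.5 says: "After Day 1, clinical safety laboratory assessments are to be collected per SOC". Protocol 4.1.1 covers intubated patients: "The following clinical assessments will be collected and analyzed as available per the institution's electronic medical records". The list that follows names intubation and extubation times, adverse events and concomitant medications. The WHO scale, ADA and Jo-1 antibody sampling continue. Safety laboratory tests are not named. Footnote 11 of the Schedule of Assessments tells sites to record standard-of-care laboratory results, but footnote 1 limits that schedule to non-intubated patients.

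**The concern.** Safety is the primary objective, and the patients are acutely ill. Some will probably have abnormal laboratory values before dosing, although the documents give no figure. For those values a three-category shift table says nothing about further deterioration in the same direction.

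Laboratory data are also the exception within the SAP. Vital signs (4.10.4), ECG intervals (4.10.5) and biomarkers (4.11.3) are all summarised as change from baseline. Chemistry, hematology and coagulation are not. The SAP's abbreviation list includes drug-induced liver injury and upper limit of normal, but no analysis in its text uses either.

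What is at stake is a comparison between arms that does not pass through investigator judgement. Without it, a drug effect that worsens an already abnormal value is visible in a table only if investigators at about 15 centres treat it as an adverse event.

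**Working it through.** The documents state no figure on this point, so there is none to reproduce. The check follows a laboratory result from the bedside to a table.

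**1. What the shift table can distinguish.** The values below are assumed multiples of the local upper limit; above 1 is high. Fold change = post-dose / baseline.

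| Baseline | Post-dose | Fold change | Shift shown |
|---|---|---|---|
| 1.5 | 1.6 | 1.6/1.5 = 1.07 | high to high |
| 1.5 | 10 | 10/1.5 = 6.67 | high to high |
| 0.8 | 1.2 | 1.2/0.8 = 1.5 | normal to high |
| 0.8 | 10 | 10/0.8 = 12.5 | normal to high |

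The first two rows fall in one cell and the last two in another. A new crossing of the limit shows, but its size does not. A value already high that rises further shows no shift. The out-of-range count has the same limit, because the patient is counted as abnormal both times.

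**2. Which value of the visit is used.** Suppose two results within one visit are 0.8 and then 10. The first-value rule records normal; a latest-value rule records high. If they are 1.2, 4 and 10, both rules record high, but the value carried is 1.2 or 10. The same-day rule in SAP 4.2 yields to 4.10.3 by its own exception. The latest-result rule below Table 3 contains no exception, so it conflicts with 4.10.3.

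**3. Which results reach a table.** After Day 1 sampling follows standard of care. Days 8, 9, 11, 12 and 13 are not scheduled visits. SAP Table 3 maps unscheduled discharge visits: Day 8 to Day 7, Days 9 to 11 to Day 10, Days 12 to 16 to Day 14. That helps only when discharge falls on such a day. The weekly assessments on Days 21 and 35 for long stays have no group of their own in SAP 4.2. Other standard-of-care results enter a summary only if the eCRF assigns them to a nominal visit, and the eCRF is not among the documents.

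**4. Against the protocol.** A count from one value per scheduled visit is narrower than a summary of all out-of-range data, and no descriptive statistics are planned for these panels. SAP 3.2 lists one change from the protocol, to the time-to-improvement endpoint. It does not mention this one.

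**5. The adverse-event route.** Protocol 8.6.5 makes clinically significant laboratory deviations adverse events. Protocol 9.1.1 adds changes requiring therapy, and says abnormal findings the investigator considers not clinically significant should generally not be recorded. Events are graded by NCI CTCAE v5.0 (Protocol 9.2.4) and tabulated by maximum severity and as grade 3 or higher (SAP 4.10.2.1). Adverse events are on the intubation list.

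**6. How likely the intubation question is to arise.** SAP 3.1.4 gives 30 patients randomised 1:1:1, so 30/3 = 10 per arm. The documents give no intubation rate p, so a range is assumed. P(at least one intubated in an arm) = 1 − (1 − p)^10:

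- p = 10%: 1 expected per arm, probability 0.65
- p = 20%: 2 expected per arm, probability 0.89
- p = 30%: 3 expected per arm, probability 0.97

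These are chances that the ambiguity matters, not estimates of lost data.

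**The case against.** A reader might infer that marked worsening would appear in no table at all. The documents do not support that. A deviation that is clinically significant or needs therapy becomes a graded adverse event, also during intubation, and TEAE incidence by severity is the primary endpoint. A new range crossing at a scheduled visit also shows.

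Nor are all laboratory data reduced to three levels. Troponins, BNP or NT-proBNP, ferritin and D-dimer appear among the safety tests in Protocol 8.6.5, and SAP 4.11.3 summarises them, with CRP and cytokines, as continuous values and change from baseline. Character results and urinalysis have their own rules.

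It would also be wrong to read the unscheduled days as a share of results lost. They are calendar days, discharge visits on them are mapped, a lasting elevation is tabulated at the next visit, and assignment depends on the eCRF.

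Likewise, omission from the list in Protocol 4.1.1 does not bar collection. Section 8.6.5 makes no exception for intubated patients, and 4.1.1 itself requires the Day 14/Discharge assessments at discharge, and weekly for stays of at least 21 days. Nothing shows that an intubated patient loses all laboratory data.

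Finally, flagged listings for about 30 patients are readable, the DSMB reviews safety data from the sixth patient dosed, and the protocol's descriptive presentation is qualified by applicability.

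All of this stands and narrows the point. It does not supply a table of magnitude for chemistry, hematology and coagulation. Listings do not compare arms, and the adverse-event route depends on the judgement that a laboratory table is meant to do without.

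**Conclusion.** The point holds in a limited form. For continuous chemistry, hematology and coagulation values, the planned laboratory tables show whether a value is outside the range, not how far. Further worsening in the same direction from an abnormal baseline produces no shift, whatever its size, and reaches a table only as a recorded adverse event. This is less than Protocol 10.1.2.3.2 describes. Standard-of-care results without a scheduled visit are only listed. Whether results during intubation are entered is unclear; that they are lost is not established.

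The number of patients or results affected cannot be derived, because the documents give no rate of abnormal baseline values, no intubation rate and no eCRF visit assignment. The multiples and intubation rates above are assumptions. This is an inexpensive improvement on the primary safety question. It does not show that the primary adverse-event analysis is invalid.

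**What to change.** 1. In SAP 4.10.3 add, for the Safety Set and by arm, a shift from baseline to worst post-dose NCI CTCAE v5.0 grade, or to multiples of the local upper limit where that suits the parameter. Use all recorded post-dose values, including unscheduled and repeat results. Add descriptive change from baseline for these panels. The protocol specifies CTCAE v5.0 for adverse events only, so the SAP must state that it now also applies to laboratory values. Label the analyses post hoc, as SAP 3.2 requires, if they are added after database lock. The Revision History shows that urinalysis grading was added after unblinding, so a late addition has a precedent.
2. Reconcile the first-value rule in 4.10.3 with the last-value and latest-result rules in 4.2, and local units with standard units.
3. State in Protocol 4.1.1 that standard-of-care safety laboratory results during intubation are entered in the eCRF. If it is too late to amend collection, report by arm how many intubated patients lack them.

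The cost is modest programming across different local ranges and some extra data entry for intubated patients. No additional sampling is needed.

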9. ADVERSE EVENTS

9.1. Definitions

9.1.1. Adverse Event

An AE is defined in the ICH Guideline for GCP as “any untoward medical occurrence in a patient or clinical investigation subject administered a pharmaceutical product and that does not necessarily have a causal relationship with this treatment” (ICH E6:1.2).

Worsening of a pre-existing medical condition, (ie, diabetes, migraine headaches, gout) is to be considered an AE if there is either an increase in severity, frequency, or duration of the condition or an association with significantly worse outcomes.

Interventions for pretreatment conditions (ie, elective cosmetic surgery) or medical procedures that were planned before study enrollment are not considered AEs.

In the case of death, only record “Fatal” for the event causing death. AEs that are ongoing at the end of the study or time of death are to be noted as “continuing.”

The Investigator is responsible for reviewing laboratory test results and determining whether an abnormal value in an individual patient represents a significant change from baseline. In general, abnormal laboratory findings without clinical significance (based on the Investigator’s judgment) should not be recorded as AEs; however, laboratory value changes requiring therapy or adjustment in prior therapy are considered AEs.

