10.1.1.2. Safety Set

The Safety Set will comprise all patients who have received any amount of study drug. Patients will be analyzed as treated.

10.1.2. Statistical and Analytical Plan for Pharmacokinetic, Pharmacodynamic, Safety and Exploratory Evaluation

A Statistical Analysis Plan (SAP) will be generated by the CRO Biostatistics Department; the SAP will be finalized prior to database lock or interim analysis if applicable and subsequent unblinding of study treatment codes. Full details of the analysis to be performed will be included in the SAP.

Any deviation from the SAP will be reported in the section “Changes in Planned Analysis” in the CSR.

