**Table 6 List of Laboratory Parameters**

Hematology	RBC WBC Basophils (absolute and %) Eosinophils (absolute and %) Lymphocytes (absolute and %) Monocytes (absolute and %) Neutrophils (absolute and %) Platelets Hematocrit Hemoglobin Mean corpuscular volume (MCV) Mean corpuscular hemoglobin (MCH) Mean corpuscular hemoglobin concentration (MCHC)
Clinical Chemistry	Total bilirubin Alkaline phosphatase Aspartate aminotransferase (AST) Alanine aminotransferase (ALT) Lactate dehydrogenase (LDH) Creatine phosphokinase Albumin Creatinine BUN Total Protein Glucose Sodium Potassium Calcium Chloride
Coagulation	Prothrombin time (PT) activated Partial thromboplastin time (PTT) International normalized ratio (INR)
Urinalysis	Hemoglobin Urobilinogen Glucose Ketones Protein Leukocyte Esterase Microscopy results: Urine RBC, Urine Squamous cell, Urine WBC
Serology (Baseline only)	Hepatitis B Virus Core Antibody Hepatitis B surface antigen (HBsAg) HIV-1 Antibody

	HIV-2 Antibody Hepatitis C antibody Hepatitis C Virus RNA
Marker of anaphylaxis	Tryptase

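### The SAP only lists creatine phosphokinase and LDH, although the protocol promises a summary of all out-of-range laboratory data, and the departure is not declared

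*SAP*

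**What the plan says.** Protocol 10.1.2.3.2 (Clinical Laboratory) first promises a listing with out-of-range values flagged. It then adds a second item: "A summary of all data outside the reference range of the clinical laboratory will be provided". It names no exempt test.

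Protocol 8.6.5 (Safety Laboratory Tests) introduces the whole panel with "The following parameters may be collected and documented in the eCRF, as available per SOC". The chemistry list runs straight through the two tests at issue: "lactate dehydrogenase (LDH), creatine phosphokinase, albumin, creatinine, blood urea nitrogen". On timing it says "After Day 1, clinical safety laboratory assessments are to be collected per SOC".

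SAP Table 6 repeats that panel: "Lactate dehydrogenase (LDH) Creatine phosphokinase Albumin Creatinine BUN Total Protein". Nothing in the table marks any of these as optional.

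SAP 4.10.3 gives the other continuous laboratory tests the number and percentage of subjects outside the normal range at each scheduled visit, plus shifts from baseline. For two tests it says instead: "Optional laboratory parameters (Creatine Phosphokinase, Lactate Dehydrogenase (LDH)) will not be summarized by treatment group, only listed".

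SAP Table 1, which records changes from the protocol, has one entry. It concerns the time-to-improvement endpoint.

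**The concern.** The protocol promises two displays, and for CPK and LDH the SAP delivers only the first. Safety is the primary objective, and a per-patient listing does not let a reader compare groups without counting by hand.

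The out-of-range table matters because of how adverse events are recorded. Under Protocol 9.1.1, "In general, abnormal laboratory findings without clinical significance" are not to be recorded as adverse events. For values of that kind, the out-of-range table is where they would be counted. For these two tests there is no such table.

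**Working it through.** There is no planned figure to reproduce. The check is a comparison of texts plus a count.

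**1. Promise against delivery, for CPK and LDH**

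| Protocol 10.1.2.3.2 | SAP 4.10.3 |
|---|---|
| Listing with out-of-range values flagged | Provided |
| Summary of all out-of-range data | Not provided; listing only |

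**2. Readings that would remove the conflict**

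- *The where-applicable qualifier in Protocol 10.1.2.3.2.* It belongs to the following sentence, on descriptive presentation, and does not limit the out-of-range summary.
- *The flagged listing is the summary.* The protocol names them as separate items, and for the other continuous tests the SAP supplies both.
- *A pooled summary remains possible.* The SAP rules out summary by treatment group but also says that the two tests are only listed, which excludes a pooled table.
- *The tests are summarized elsewhere.* SAP 4.11.3 (Biomarker) covers troponins, BNP, NT-proBNP, ferritin and D-dimer, but neither CPK nor LDH.
- *The tests have a different collection status.* In Protocol 8.6.5 the standard-of-care condition governs the whole panel.

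**3. Count, from SAP Table 6**

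- Hematology 13, chemistry 15, coagulation 3, urinalysis 9: 13 + 15 + 3 + 9 = 40 parameters.
- Share of chemistry without the summary: 2/15 = 13.3%.
- Share of all 40 parameters: 2/40 = 5.0%.

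**4. Are these two unique?**

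The other 13 chemistry tests (15 − 2), hematology and coagulation all fall under the SAP 4.10.3 summaries. Troponins, BNP or NT-proBNP, ferritin and D-dimer, also named in Protocol 8.6.5, get descriptive values and change from baseline in SAP 4.11.3. That leaves CPK and LDH as the only quantitative blood tests in Protocol 8.6.5 with no planned summary. (Tryptase is also only listed, but it is not in the 8.6.5 list.)

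**5. Patients affected**

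The documents give neither a testing rate nor an out-of-range rate for CPK or LDH, so no number of patients can be stated. The ceiling is the trial size: 30 patients, about 10 per arm.

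**The case against.** The best defence is delegation and disclosure. Protocol 10.1.2 says "Full details of the analysis to be performed will be included in the SAP", and SAP 4.10.3 states its rule openly. The protocol sentence is general: it defines no layout, no visit structure and no split by arm. The SAP was also written against an eCRF that is not available here and that may mark these fields optional.

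Part of this stands. A reader might infer concealment, or a rule introduced once treatment codes were known. The documents support neither: the rule is in plain view, and the SAP Revision History does not list it among the changes made after unblinding. The absence of a visible reason also does not show that there was none. But leave to supply detail is not leave to drop an explicit commitment, and the protocol makes no exception for optional fields.

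A second objection is that, read literally, the protocol sentence also reaches troponins, BNP or NT-proBNP, ferritin and D-dimer, which get no out-of-range summary either. That is correct. It means that CPK and LDH should not be described as the only tests lacking an out-of-range table. They are the only ones lacking any summary.

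A third objection is that the protocol sentence does not ask for shift tables or a by-arm split. That also stands. Presenting the counts by arm follows from using the SAP's existing table, not from the protocol.

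A reader might also want percentages for these two tests based on patients tested. That is unnecessary. All safety laboratory testing after Day 1 follows standard of care, SAP 4.2 already has categorical summaries show the number of patients providing data, and a separate denominator would make these two tests non-comparable with the rest of the table.

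**Conclusion.** The point holds as an undeclared conflict between Protocol 10.1.2.3.2 and SAP 4.10.3, of minor consequence. It affects 2 of 15 chemistry tests.

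A reader might infer that the primary safety analysis is compromised. It is not. All CPK and LDH values are listed with abnormal ones flagged, and Protocol 8.6.5 requires clinically significant deviations to be recorded as adverse events, so those arising after dosing reach the treatment-emergent adverse event tables. The loss is confined to abnormal values not judged clinically significant, which go uncounted.

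The conclusion rests on reading the protocol's promise of a summary as separate from its promise of a listing, which is how the section is written. It does not depend on what the eCRF says, since the protocol sentence has no carve-out for optional fields.

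**What to change.** Delete the sentence on optional laboratory parameters from SAP 4.10.3. CPK and LDH then enter the existing out-of-range summary (number and percentage outside the normal range, by scheduled visit and treatment group) under the same rules as the other chemistry tests, with the number tested shown as SAP 4.2 already provides. Shift tables for the two tests are optional.

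Label the added output as introduced after unblinding, because the current SAP version itself postdates unblinding.

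If the sponsor prefers listing only, the lesser remedy is to declare and justify the departure in SAP Table 1 and in the study report.

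The data are already collected. The cost is one extra block per test per visit. SAP 4.2 groups by-visit summaries into 11 days (1 to 7, 10, 14, 28 and 60), so the upper limit is 2 × 11 = 22 blocks. Fewer will be populated, since laboratory tests after Day 1 are done per standard of care during hospitalization. For the same reason the number tested at a visit may be low, and some blocks will say little.
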